An Open-label Study to Investigate the Efficacy and Tolerability of Aczone Gel, 7.5% in the Treatment of Acne Vulgaris in Men and Women With Skin of Color

[name]

NCT03681470

Document Date: Feb 7, 2022

Protocol Document for 17-01277
Principal Investigator: [name].
Mount Sinai

Brief Summary of Research

Acne vulgaris is a common skin disease characterized by inflammatory papules, pustules, and comedones that is prevalent in men and women of color. Research has demonstrated that Aczone[®] (dapson) gel, 7.5% used once daily is effective, safe, and well-tolerated for the treatment of acne in both men and women; however, no data is available regarding its efficacy and safety in skin of color (SOC). The current study aims to investigate the therapeutic impact of Aczone gel 7.5% in SOC males and females ages 18 and older with acne vulgaris. The study will also evaluate the impact of Aczone[®] gel on hyperpigmentation and PIH of the face.

Objectives

The purpose of this study is to evaluate the safety and efficacy of Aczone[®] gel, 7.5% administered once daily for 24 weeks in males or females with skin of color (SOC), defined as Fitzpatrick Skin Types IV, V, or VI, for the treatment of facial acne vulgaris.

Background

Acne vulgaris is a common skin disease characterized by inflammatory papules, pustules, and comedones that is prevalent in men and women of color. In fact, acne is the most common dermatologic diagnosis made in SOC populations (1). Although individuals of all skin types can develop acne vulgaris, there are important differences in darker skin types that are important to consider when choosing an optimal treatment (2).

From a diagnosis standpoint, acne in women of color is more likely to present on the cheek area, as opposed to a chin and cheek predominance in white women (2). Complications from acne are of great concern in this population, as women of color are more likely to develop keloids, hypertrophic scars, and post-inflammatory hyperpigmentation (PIH) as a result of acne lesions (3). PIH may last for weeks to months and, in many cases, is more troublesome to patients than the acne itself (2). Overall, facial acne and its sequelae have a greater impact on perception of appearance, negative emotions, and social functioning in women of color than white women (2).

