4. Subjects with a history of clinically significant hemolysis, anemia, or enteritis (regional enteritis, ulcerative colitis, pseudomembranous colitis, antibiotic-associated colitis)
5. Subjects with allergy or sensitivity to the study drug or its components
6. Subjects who have not complied with the proper wash-out periods:
 - a. Topical anti-inflammatory medications, salicylic acid, corticosteroids, antibiotics, antibacterials, peroxide-containing products, or retinoids within 2 weeks of baseline
 - b. Systemic antibiotics, corticosteroids, antimalarials or oral dapsone within 4 weeks of baseline

- c. Other anti-acne medication, including isotretinoin or spironolactone, within 6 months of baseline
 - d. Chemical peels or other facial acne procedures (laser therapy, light therapy) within 3 months of baseline
 - e. Treatment with botulinum toxin of any serotype in the face within 6 months of baseline
 - f. Estrogens/Birth control pills must have been started ≥ 90 days prior to baseline and use must be continued during the study without alteration or discontinuation.
7. Pregnant or breastfeeding.
 8. Subjects with evidence of alcohol or substance abuse.
 9. Use of any investigational drug within 4 weeks prior to randomization, or 5 pharmacokinetic/pharmacodynamic half-lives, if known (whichever is longer).

c) Number of Subjects

Up to 40 subjects with acne vulgaris will be screened with a goal of 20 total subjects randomized. All 20 randomized subjects are expected to complete all study procedures. Individuals who provide informed consent and fail to meet all of the inclusion and exclusion criteria during the initial evaluation will be considered a “screening failure.”

d) Study Timelines

The study will consist of 6 in-person visits and one phone visit (7 total visits) over up to 28 weeks (4 week screening period plus 24 weeks enrolled in study). Study visits will be conducted at Screening (Visit 1), Baseline (Visit 2, Week 0), Week 4 (Visit 3), Week 8 phone visit (Visit 4), Week 12 (Visit 5), Week 18 (Visit 6), Week 24 (Visit 7).

Enrollment will occur over a 24-36 month period from January 2018 to December 2020. The study is anticipated to be completed by December 2021.

e) Endpoints

Primary Endpoint:

1. Mean change from baseline to week 12 in Global Acne Assessment Score (GAAS)

Secondary Endpoints:

1. Change from baseline in Global Acne Assessment Score (GAAS) at week 4, 18, and 24.

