2. Change from baseline in Post Acne Hyperpigmentation Index (PAHPI) at weeks 12, 18, and 24.
3. Change from baseline in Melanin Index (MI) of target lesion at weeks 12, 18, and 24
4. Change from baseline in the proportion of subjects with score of 0 or 1 on ASIS “dark spot” score at weeks 4, 12, 18, and 24.
5. Proportion of subjects with GAAS of 0 (none) or 1 (minimal) at weeks 4, 12, 18, and 24

6. Percent change from baseline in all lesion counts (inflammatory, noninflammatory, and total) at weeks 4, 12, 18, and 24.

f) Procedures Involved in the Human Research

This is a single-center, single-group, open-label study using Aczone® (dapson) gel 7.5%. All subjects will receive the study medication. Aczone® gel is an off-white to yellow gel with suspended particles. It is supplied in an airless pump containing a polypropylene bottle with a high density polyethylene piston. It will be dispensed as a 60g pump.

Subject will apply Aczone® once daily to the entire face. Study drug must not be applied to other areas of the body, including the upper chest, upper back or shoulders.

Prior to the start of the study, potential subjects will be given an IRB-approved Informed Consent Document (ICD) containing a Health Insurance Portability and Accountability Act (HIPAA) disclosure agreement to read, understand, and sign. All questions about the study should be answered to the satisfaction of the candidate subject. They will have all of their study-related questions answered by the PI or designee, and if they agree to participate, the subject will sign two original copies of the ICD. The subjects will retain one original copy and one original copy will be kept in the study file. The subjects who sign an ICD will be assigned a screening number.

After providing informed consent, subjects will be assessed for study eligibility at the Screening visit (day -28 to day -1), which includes review of medical history and concomitant, acne lesion counting and severity ratings, and serum pregnancy test (if applicable). The PI or a medically qualified designee must review this information (i.e. medical history, concomitant medication, and eligibility review) for each subject to confirm their eligibility before enrollment. A total of 20 subjects who meet eligibility criteria will undergo Baseline / Day 0 assessments. Subjects will return for visits at weeks 4, 12, 18, and 24. There will be a phone visit at week 8.

Study Assessments and Efficacy Measures:

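### Neither Exclusion 6 nor any on-study rule addresses skin-lightening products or non-acne pigment procedures, although three secondary endpoints measure hyperpigmentation

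*Combined protocol and SAP*

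**What the plan says.** **Aim and endpoints.** The Brief Summary states, "The study will also evaluate the impact of Aczone", and goes on to name hyperpigmentation and PIH of the face. Three of the six secondary endpoints in section e) measure this:

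- "Change from baseline in Post Acne Hyperpigmentation Index (PAHPI) at weeks 12, 18, and 24"
- "Change from baseline in Melanin Index (MI) of target lesion at weeks 12, 18, and 24"
- "Change from baseline in the proportion of subjects with score of 0 or 1 on ASIS “dark spot” score" (four visits, the first at week 4)

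**Wash-outs.** Exclusion 6a covers "Topical anti-inflammatory medications, salicylic acid, corticosteroids, antibiotics, antibacterials, peroxide-containing products, or retinoids within 2 weeks of baseline". Item 6b covers systemic drugs. Item 6c covers "Other anti-acne medication, including isotretinoin or spironolactone, within 6 months of baseline". Item 6d covers "Chemical peels or other facial acne procedures (laser therapy, light therapy) within 3 months of baseline". Items 6e and 6f cover facial botulinum toxin and estrogens or birth control pills.

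**During treatment.** Concomitant medications and procedures are recorded at all seven visits (Table 1). The text seen contains no list of products to be avoided after baseline.

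**Design and analysis.** Section f) says: "This is a single-center, single-group, open-label study using Aczone® (dapson) gel 7.5%. All subjects will receive the study medication". The analysis of secondary endpoints treats movement off the diagonal of the baseline-by-visit table as evidence of a treatment effect. It uses paired t-tests with a Bonferroni correction and Wilcoxon signed-rank tests in parallel, and adds an ordinal logit model with time points, age and gender.

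**The concern.** The wash-out list is built around acne treatment, while half of the secondary endpoints concern pigment. A subject who starts a lightening cream shortly before baseline and uses it to week 24 meets every stated criterion and breaks no stated rule, unless the cream contains an agent listed in 6a or counts as anti-acne medication under 6c. The same holds for a pigment-directed laser procedure that is not an acne procedure.

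With one group and no covariate for other products, any fading such use causes enters the change from baseline and is read as an effect of the gel. Use stopped just before baseline could work in the opposite direction, through re-darkening. At stake is the reading of PAHPI, melanin index and the dark-spot score. The Background presents these as an open question, because the earlier signal with the 5% gel was anecdotal.

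**Working it through.** **1. What the eligibility text covers.**

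| Item | Reaches | Does not reach |
|---|---|---|
| 6a | Products containing a retinoid, corticosteroid, salicylic acid or another listed topical | A lightening product without a listed ingredient |
| 6c | A lightening product that is also anti-acne medication | A product used only for dark spots |
| 6d | Chemical peels; facial acne procedures | A pigment-directed procedure that is neither |
| On-study rule | None found in the text seen | Use begun after baseline |

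Coverage is therefore partial. A wash-out entry alone would not close the gap, because it does not govern use begun after Day 0.

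**2. The plan's own figure.** The only stated calculation is power above 90% for a 1-point GAAS change (SD 0.513, n = 20, two-sided 5%). With 0.513 as the SD of change, noncentral-t power exceeds 99.99%, so the statement reproduces. It concerns the primary endpoint and is not touched by this point. The plan gives no figure for the pigment endpoints.

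**3. Noise-free illustration on PAHPI (assumed, not from the documents).** Let the gel have no effect on pigment. Let k of 20 subjects drop one intensity step (3 points in the PAHPI table) because of a lightener, and let the rest not change. The mean change is −3k/20. The paired t statistic, in absolute value, is √(19k/(20 − k)), whatever the step size.

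The Bonferroni family is not stated. Counting endpoint-by-visit tests for the first group of secondary outcomes gives GAAS 3 + PAHPI 3 + MI 3 + dark spot 4 + GAAS 0/1 4 = 17. Adding three lesion counts at four visits (12) gives 29.

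| k | Mean change | t (df 19) | Unadjusted p | p × 17 | p × 29 |
|---|---|---|---|---|---|
| 7 | −1.05 | 3.20 | 0.0047 | 0.080 | 0.137 |
| 8 | −1.20 | 3.56 | 0.0021 | 0.036 | 0.061 |

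So 8 of 20 (40%) are needed with 17 tests, and 8 are not enough with 29. A narrower family of 9 (three pigment outcomes at three visits) would need 7 (0.0047 × 9 = 0.043). The exact Wilcoxon p for 8 changes of one sign is 2 × 0.5⁸ = 0.0078, or 0.13 after × 17, so the parallel test would not agree.

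**4. With noise (also assumed).** Take SD of change 1, no gel effect, and users fading by 1.0 to 1.5 SD. The bias in the mean is k × effect/20. The chance of a false significant improvement comes from 40,000 simulated trials per setting, with 9 tests as the Bonferroni divisor.

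| k | Bias in mean (SD) | False improvement, 9 tests |
|---|---|---|
| 0 | 0 | 0.3% |
| 4 | 0.20–0.30 | 1.6–2.3% |
| 8 | 0.40–0.60 | 7–16% |

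The multiplicity correction keeps false significance uncommon at modest use. It does nothing to the bias in the reported mean change.

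**The case against.** **Use is not documented.** The Background says PIH can trouble patients more than acne. A reader might infer that lightener use is likely in this population, but the protocol says nothing about such products and gives no rate. This stands: the bias is conditional and of unknown size.

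**A few users would not produce a positive finding.** A reader might infer that a handful of users is enough for a false significant result. The plan's own rules do not support that, because the secondary t-tests are Bonferroni-adjusted and the Wilcoxon test runs beside them. This stands for significance. It does not stand for the estimate, which shifts in proportion to the number of users.

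**Safeguards exist.** Items 6a, 6c and 6d catch some products and procedures. Concomitant medication is reviewed before enrolment and recorded at every visit. This stands in part. Recording is not restricting, no analysis uses the record, and a cosmetic product may go unreported unless asked about. The mexameter also reads adjacent uninvolved skin, but the endpoint is defined on the target lesion and no correction is specified.

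**An on-study rule may exist elsewhere.** The subject instruction sheet is not part of the protocol. The text between the data-management and monitoring sections was not available here. Neither can be assumed to contain or to lack a restriction.

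**The fix does not make fading attributable.** By the protocol's own account PIH lasts weeks to months, so spontaneous fading over 24 weeks affects every subject. This stands fully, but it is no reason to leave in a confounder that can be removed cheaply.

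**Conclusion.** The concern holds as an avoidable gap. Lightening products and non-acne pigment-directed procedures are addressed neither before baseline nor during treatment, while three secondary endpoints and a stated aim depend on pigment change in a single group. The bias can run in either direction and affects only PAHPI, melanin index and the dark-spot score; the primary GAAS endpoint is untouched.

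Its size cannot be stated from the documents. The figures of about 8 users, and of 0.20 to 0.60 SD bias for 4 to 8 users, rest on assumed numbers of users, effects and test families. They show scale only and do not predict a false result. Nor do the documents support reading any observed fading as mainly due to lighteners. The lack of a control is the larger limit on attribution. The change is worth making because it is cheap and protects a declared aim.

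**What to change.** - **Eligibility and conduct.** Add topical depigmenting or skin-lightening products, and pigment-directed facial procedures, to Exclusion 6 and to an explicit on-study restriction. The sponsor sets the wash-out length and the on-study rule. Inclusion 9 already limits ultraviolet exposure throughout the study, so a rule of this kind fits the protocol's format.
- **Data collection.** At the existing concomitant-medication check, ask about these products by name, including over-the-counter ones, and record start and stop dates.
- **Analysis.** Repeat the PAHPI, melanin index and dark-spot analyses without readings taken after such use. Report the number of users beside the main result.
- **Interpretation.** State that spontaneous fading of PIH cannot be separated from drug effect in this design.

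The cost is one eligibility line with its on-study counterpart, one prompt on an existing form and one sensitivity analysis. The downside is that a few candidates are delayed or screened out. If enrolment has closed, as the planned dates suggest, the analysis step can still be applied to whatever use was recorded.

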Global Acne Assessment Score (GAAS):

The subject's acne severity will be assessed by the investigator using a 5-point GAAS at screening, baseline, and weeks 4, 12, 18, 24.

Grade	Description
0	None No evidence of facial acne vulgaris
1	Minimal Few noninflammatory lesions are present; a few inflammatory lesions (papules/pustules) may be present; no nodulo-cystic lesions present
2	Mild Several to many noninflammatory lesions are present; a few inflammatory lesions are present; no nodulo-cystic lesions present.
3	Moderate Many noninflammatory and inflammatory lesions are present; no nodulo-cystic lesions are present.
4	Severe Significant degree of inflammatory disease; papules and pustules are a predominant feature; a few nodulo-cystic lesions are present (no more than 2)

Lesion Counts:

The lesion counts, including inflammatory and non-inflammatory lesions, will be performed at screening, baseline, and weeks 4, 12, 18, and 24. Inflammatory lesions (papules, pustules, nodules/cysts) and

noninflammatory lesions (open comedone, closed comedone) will be counted individually. The sum of the inflammatory lesion counts and non-inflammatory lesion counts will be totaled.

ASIS ®:

Acne Symptom and Impact Scale (ASIS ®) will be given to subjects' for completion at baseline and weeks 4, 12, 18, and 24. The ASIS ® contains 9 items assessing symptom severity and 8 items assessing the psychosocial impact of acne vulgaris (6). High scores on the ASIS® indicate the presence of more severe symptoms, whereas higher scores on the ASIS indicate better outcomes on acne health-related quality of life.

PAPHI:

The postacne hyperpigmentation index (PAHPI) has been shown to be a reliable and valid score measuring post-inflammatory hyperpigmentation from acne (7). PAHPI will be scored using the following formula:

Total PAHPI = S + I + N

PAHPI Score can range from 6-22.

Lesion Size (S)

Weighted Score (S)	Median Lesion size
2	<3mm
4	3-6mm
6	7-10mm
8	>10mm

Lesion Intensity (I)

Weighted Score (I)	Median Lesion Intensity
3	Slightly darker than surrounding skin
6	Moderately darker than surrounding skin
9	Significantly darker than surrounding skin

Lesion Number (N)

Weighted Score (N)	Number of Lesions
1	1-15
2	16-30
3	31-45

4	46-60
---	-------

5	>60
---	-----

Melanin Index:

A narrowband reflectance spectrophotometer (mexameter MX-16) will be used to measure the degree of pigmentation of involved and adjacent uninvolved skin of one representative facial PIH lesion (8).

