- Skin phototype assessment (Fitzpatrick Skin Type)
- Lesion Counting
- Global Acne Assessment Score (GAAS)
- Adverse events
- Urine pregnancy

Baseline

- Inclusion/Exclusion
- Adverse events
- Concomitant medications and procedures
- Lesion Counting
- Melanin index

- GAAS
- Post Acne Hyperpigmentation Index (PAHPI)
- ASIS dark spot score
- Local tolerability assessment
- Photography
- Urine pregnancy
- Product dispensation/return

Week 4 –

- Adverse events
- Concomitant medications and procedures
- Lesion Count
- GAAS
- ASIS dark spot score
- Local tolerability assessment
- Pregnancy test
- Product dispensation/return

Week 8 Phone Visit –

- Adverse events
- Concomitant medications and procedures

Week 12 –

- Adverse events
- Concomitant medications and procedures
- Lesion Counting
- GAAS
- PAHPI
- ASIS dark spot score
- MI
- Photography
- Local tolerability assessment
- Product dispensation/return
- Urine pregnancy test

Week 18 –

- Adverse events
- Concomitant medications and procedures
- Lesion Counting
- GAAS
- PAHPI
- ASIS dark spot score
- MI
- Photography
- Local tolerability assessment
- Product dispensation/return
- Urine Pregnancy test

Week 24 –

- Adverse events
- Concomitant medications and procedures
- Lesion Counting
- GAAS
- PAHPI
- ASIS dark spot score
- MI
- Photography
- Local tolerability assessment
- Product return
- Urine Pregnancy test

Table 1: Assessment Schedule

Visit	1	2	3	4	5	6	7
Week	-4 to BL	0 (BL)	4	8 phone	12	18	24
Visit Window (days)			±3	±3	±3	±3	±3
Assessment							
Informed Consent	X						
Demographics	X						
Inclusion/Exclusion	X	X					
Medical History	X						
Fitzpatrick Skin Type	X						
AE/SAE assessment	X	X	X	X	X	X	X
Concomitant medications	X	X	X	X	X	X	X
Concomitant procedures	X	X	X	X	X	X	X
Photography		X			X	X	X
Urine Pregnancy Test	X	X	X		X	X	X
Lesion Count	X	X	X		X	X	X
GAAS	X	X	X		X	X	X
ASIS ®		X	X		X	X	X
PAHPI		X			X	X	X
Mexameter – Melanin Index		X			X	X	X
Local tolerability		X	X		X	X	X
Study Drug Dispensation and Return		X	X		X	X	X

g) Specimen Banking

Not applicable.

h) Data Management and Confidentiality

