At each time point, the changes from baseline in ordinal secondary endpoints GAAS, PAHPI, MI, the proportion of subjects with a score of 0 or 1 on ASIS “dark spot,” the proportion of subjects with $GAAS < 2$ will be presented in frequency tables. The (i,j) entries in the tables are counts of subjects in category i at baseline that moved to category j at that time point. A high frequency of counts falling off the main diagonal of the table is evidence in favor of a significant treatment effect. Similarly, to the primary endpoint, we will apply a two-sided paired t-test to assess the significance of changes from baseline in each outcome. We will apply the Bonferroni correction to adjust for the multiplicity of tests. In parallel, we will test pre vs. post differences in these ordinal outcomes with the Wilcoxon Signed Rank test. Discrepancies between the parametric and non-parametric approaches will be discussed on a case basis. In addition to this approach, we will fit an ordinal logit model, including all available time points, age, and gender as covariates.

The changes from baseline in lesion counts (inflammatory, non-inflammatory, and their aggregation) will be assessed with the two-sided paired t-test followed by Bonferroni correction. A Generalized Linear Mixed Model (GLMM) will be fitted to model the count of lesions as the dependent variable, time and inflammation as fixed effects, age, and gender as covariates. In this framework, we will include random intercept and slope for each subject’s trajectory. The contrasts will reveal differences between time points and treatment effect in inflammatory vs. non-inflammatory lesions.

Missing Data and Outliers

Missing data in the longitudinal data analysis will be handled by the mixed-effects approach which performs an appropriate adjustment of the coefficients’ degrees of freedom for each fitted model. We do not foresee issues with outliers due to the endpoints’ measurement level, most of them being ordinal.

Reference:

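### The ASIS dark-spot score is collected at five visits, but only the 0-or-1 proportion is tested, so the planned ordinal methods cannot use the grades

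*Combined protocol and SAP*

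**What the plan says.** Section e) Endpoints, secondary endpoint 4, is "Change from baseline in the proportion of subjects with score of 0 or 1 on ASIS" dark spot, at weeks 4, 12, 18 and 24. No listed endpoint uses the score itself.

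Section k), Analysis of secondary Endpoints, carries forward "the proportion of subjects with a score of 0 or 1 on ASIS" dark spot as one of a list of outcomes described as ordinal. Frequency tables, a two-sided paired t-test and a Bonferroni correction apply to that list. The section then adds: "we will test pre vs. post differences in these ordinal outcomes with the Wilcoxon Signed Rank test". An ordinal logit model with time, age and gender follows, and it names no other ASIS outcome.

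The grades are collected. Section f) gives the ASIS to subjects "for completion at baseline and weeks 4, 12, 18, and 24", and the visit schedule lists "ASIS dark spot score" at each of those visits. Section f) says that the instrument "contains 9 items assessing symptom severity and 8 items assessing the psychosocial impact of acne vulgaris", but not how many response levels the dark-spot item has.

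**The concern.** Cutting the score at 0 or 1 has two effects. A subject who improves without crossing the cut counts as unchanged. A subject already at 0 or 1 at baseline cannot improve, and no entry criterion requires dark spots at baseline. With a target of 20 subjects, both losses matter.

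The plan handles its other graded outcomes differently. GAAS also has a 0-or-1 proportion (endpoint 5), but its graded form is the primary endpoint and secondary endpoint 1. PAHPI and melanin index are analysed as changes in value. Among the hyperpigmentation outcomes, only the dark-spot item is tested solely as a cut, and it is the only one that subjects complete themselves. What is at stake is the sensitivity of the patient-reported view of hyperpigmentation.

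**Working it through.** **Inputs from the documents.** Section c): n=20, single group, no dropout planned ("with a goal of 20 total subjects randomized"; "All 20 randomized subjects are expected to complete all study procedures"). Section k): two-sided paired t-test, 5% level, Bonferroni with no family defined.

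**Inputs assumed, because the documents do not give them.** Number of item levels, baseline distribution, within-subject correlation and size of shift.

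**1. The plan's own power figure.** It concerns GAAS only: 1 point, SD 0.513, n=20. The noncentrality is (1/0.513)×√20 = 8.72, so power exceeds 99.9% if 0.513 is the SD of the difference. In the extreme case of an SD of the difference of 2×0.513 = 1.026, power is 98.5%. The stated figure of more than 90% holds, but it says nothing about ASIS.

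**2. What the planned methods become on a 0/1 variable.** The paired differences are −1, 0 or +1. The non-zero differences all tie in size, so the signed-rank test reduces to a sign (McNemar-type) test. An ordinal logit with two levels is a binary logit. Neither recovers the grades.

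**3. How many subjects must cross.** If k of 20 cross to 0 or 1 and none reverse, the paired t statistic is t = √[19·q/(1−q)] with q = k/20 and 19 df. The exact McNemar p-value is 2×0.5^k.
- k=4: t=2.18, p=0.042
- k=6: t=2.85, p=0.010; McNemar p=0.031
- k=8: t=3.56, p=0.0021; McNemar p=0.0078
- k=9: t=3.94, p=0.0009
- k=11: McNemar p=0.00098

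The minimum is therefore 4, 6 and 9 crossings (paired t-test) or 6, 8 and 11 (McNemar) at 0.05, 0.0125 and 0.05/29 respectively.

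**4. The Bonferroni thresholds.** Two families bracket the unstated one. The four ASIS visits give 0.05/4 = 0.0125. All secondary endpoint-by-visit tests number 3+3+3+4+4+(3×4) = 29, giving 0.05/29 = 0.0017. Both are assumptions.

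**5. Power, indicator against score.** Simulation: baseline latent z is standard normal; follow-up latent is ρz + √(1−ρ²)e − shift, with e standard normal. Both are cut at the same points into an assumed 0–4 item, with n=20 and ρ=0.6. Three baseline patterns were used: 18% at 0 or 1, 35% at 0 or 1, and a cluster at 1–2 (3/32/60/4/1% across levels 0 to 4). Paired t-test power across patterns:

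| Latent shift | Level | 0-or-1 indicator | Item score |
|---|---|---|---|
| 0.6 SD | 0.05 | 39–43% | 59–74% |
| 0.8 SD | 0.05 | 62–68% | 84–93% |
| 0.8 SD | 0.0125 | 38–45% | 63–80% |
| 0.8 SD | 0.05/29 | 9–14% | 33–52% |

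The low end of each score range comes from the clustered pattern. There the gap at 5% is about 16 points at 0.6 SD (43% against 59%) and 11 points at 1.0 SD (85% against 96%).

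**6. Sensitivity.** A wider grid used correlation 0.3 to 0.7, baseline share at 0 or 1 of 5% to 50%, and shifts of 0.4 to 1.0 SD. The indicator had lower power at 5% in all 48 settings, by roughly 10 to 65 points, and lost most when few subjects start at 0 or 1. The number of levels matters less: at 0.8 SD and 5%, a 4-level item gives 67% against 90% and an 11-level item 63% against 94%.

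**The case against.** A responder proportion is a legitimate endpoint. It reads more directly than a mean change and parallels the GAAS 0-or-1 proportion, so the choice of form is partly preference. The hyperpigmentation aim does not hang on it: the Background names PAHPI and melanin index for that purpose, and both are tested uncut at weeks 12, 18 and 24. The study is open-label with one group, so a sharper test of a self-report still shows only before-after change. The authors may also have meant to model the score, since they call the list ordinal. All of this stands except the last point: section k) lists graded GAAS separately from its proportion, but for ASIS it names the proportion alone.

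A reader might infer that a real shift will probably be missed, and that the cut buys nothing. The documents do not support that. Under the assumptions above, the indicator has more than 60% power at 0.8 SD and 82–85% at 1.0 SD at the 5% level, and it gives a readable percentage. A reader might also blame the cut for the very low power at 0.05/29. Much of that loss comes from the assumed family: the score itself reaches only 33–52% there at 0.8 SD.

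**Conclusion.** The point holds as a minor one. As written, the plan tests the dark-spot item only as a two-level variable, and its ordinal methods cannot use the grades collected. That much follows from the text alone.

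The direction of the power loss was the same in every pattern tried, but its size depends on assumptions. In the main settings at 5% it ranges from about 11–16 points, with baseline scores clustered near the cut, to about 30 points or slightly more with more spread scores. It would be small if nearly all change were a single step from 2 to 1. The consequence is confined to the sensitivity of one secondary, subject-reported endpoint. It does not undermine the primary analysis or the evaluation of hyperpigmentation as a whole.

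**What to change.** In sections e) and k), name the change from baseline in the ASIS dark-spot item score at weeks 4, 12, 18 and 24 as the tested outcome, using the paired test, signed-rank test and ordinal model already planned. State the item's response range and the Bonferroni family. Keep the 0-or-1 proportion at each visit as a responder summary with an exact interval.

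Timing matters: the document is dated February 2022 and section d) anticipated completion by December 2021. If outcome data have already been seen, leave endpoint 4 in place and add the graded analysis as a labelled post hoc supplement.

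The cost is wording and a short analysis, with no new data or visits. The small downside is that a mean or ordinal change is less directly read than a percentage, which is still reported.
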